The purpose of this study is to evaluate the effectiveness of a multicomponent training protocol (MCT) on the following parameters: psychological, physical fitness, mental well-being, and quality of life, in cancer survivors currently in a stabilized condition, compared to an aerobic training protocol (AT) and a waiting control group (WLCG). In addition, the aim is to evaluate the impact of training in participants' coping strategies, i.e., the ways in which they manage stress, emotional difficulties and daily challenges, in order to foster better psychological adaptation and greater autonomy.

Secondary outcome:

To assess adherence to protocols through analysis of dropout rates and number of sessions completed.

Hypothesis

We hypothesize that both groups will demonstrate improvements in physiological parameters, physical fitness, mental well-being, and overall quality of life compared to the WLCG. Furthermore, the MCT group is expected to achieve greater enhancements in physiological parameters than the AT group. Additionally, the MCT group is anticipated to have a more significant impact on strengthening coping strategies, promoting better stress management, and fostering more effective psychological adaptation.

PARTICIPANTS

The study aims to recruit at least 60 cancer survivors currently in physiological or chronic-stabilized condition between 18-80 years of age.

Inclusion criteria.

- Women/Men;
- Age between 18 and 80 years at the time of initial treatment;
- Subjects in remission for at least 3 months;
- No diagnosis of secondary cancer at baseline;
- No physical impediment to physical activity (Eastern Cooperative Oncology Groups (ECOG) performance status 0-1);
- Signature of a written informed consent form (or their legally recognized representatives must sign) indicating that the patient understood the purpose and procedures required for the study and is willing to participate in the study;
- Sedentary lifestyle (subjects who have not followed WHO guidelines for aerobic and resistance exercise in the past 3 months).
- Currently in treatment, as long as not hospitalized, in stabilized chronic condition,
- Positive medical specialist assessment of noncompetitive physical activity practice.

Exclusion criteria.

- Metastasis;
- Uncontrolled hypertension or untreated heart disease;

- Severe musculoskeletal or joint disorders with severe mobility limitations;
- Psychiatric disorders;
- Taking psychotropic drugs;

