- Inability to engage in physical activity;
- Lack of fitness to practice sports.
- Expected absence of more than two weeks during the intervention period.

SAMPLE NUMEROSITY

G*Power software (version 3.1) was used to determine the sample size needed to ensure adequate statistical power.

The calculation was performed assuming a mean effect (with a value of 0.25 for effect size f), which is a value commonly used in studies of similar size. A significance level of 0.05 was set and a statistical power of 85% (0.85) was adopted, which is generally considered an adequate value to minimize the risk of type II errors.

For the calculation, two groups (multicomponent training and aerobic training) and two measurement times (before and after the intervention) were considered. An average correlation (0.5) was estimated between the repeated measurements on participants, as it is expected that the collected data are fairly correlated between the different surveys. Finally, it was assumed that there were no violations of sphericity by setting a correction for nonsphericity equal to 1.

Based on these parameters, the calculation indicated the need for a sample size of 32-40 total participants, with 16-20 participants per group, to ensure sufficient statistical power to detect any significant effects.

PROCEDURES

Participants will be recruited through days dedicated to raising awareness and promoting the project, also organized in the area in collaboration with relevant bodies, associations and health facilities. During these events, detailed information will be provided on the objective of the study, potential benefits, and how to participate. Informational materials, such as brochures and posters, will also be used and distributed at major gathering places. Then participants will be randomly assigned to one of three groups:

- MCT
- AT

- WLCG

Data collection

Prior to the intervention, all subjects will sign an informed consent upon authorization from their attending physician. All subjects will participate in physiological assessments, functional and psychological tests before (T0) and at the end of the intervention (T1). Data will be collected anonymously by assigning each participant a random ID number.

Measurements:

Anthropometric parameters:

- Height
- Weight
- BMI
- BIA

Physical parameters:

- Timed Up and GO (TUG);
- 30 Seconds Chair Stand Test (30" CST);
- 2 Minutes Step Test (TMST);
- Back Stretch Test;
- Chair Sit and Reach Test;

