- Handgrip Strength Test (HGS).

Psychological Parameters:

- The State-Trait Anxiety Inventory (STAI-Y);
- Beck Depression Inventory (BDI);
- Fatigue Severity Scale (FSS);
- The EORTC Core Quality of Life questionnaire (EORTC QLQ-C30);
- Brief COPE.

Experimental Design

After initial evaluations, subjects will be randomly assigned to one of two groups. All protocols will last 24 weeks and will be conducted at the Angiulli Artistic Gymnastics Society (Bari).

Sessions will be conducted in small groups. These groups will be closely supervised by exercise professionals, adapted physical activity (AFA) specialists to ensure the safety of the participants, maintain the right level of intensity, and correct execution technique. To monitor and adjust the training intensity (internal load) during the ongoing sessions, Borg's Fatigue Perception Scale (RPE) (6-20) (Borg, 1982) will be used at the end of each exercise set to adjust the load in Borg = 10-15 points (Gary Liguori & American College of Sports Medicine (ACSM), 2021). Participants will be previously familiarized with the scale.

Participants in the WLCG will not perform any structured physical activity during the entire intervention period, maintaining their usual lifestyle and placed on a waiting list to receive adapted physical activity after the 24-week intervention period.

Multi-component Training:

Each training session will include an initial 10-minute muscle activation phase (low-intensity walking, Borg = 10-11) to increase heart rate, improve muscle blood flow, and prepare the major joints for the next phase of work, a 40-minute main period of exercise (aerobic exercise, mobility exercises, and resistance training), and a 10-minute defatigue period (breathing and stretching exercises). Cardiorespiratory training will consist of progressive aerobic exercises: controlled and rhythmic jumping jacks, step-ups on a stable platform (such as a low step or stable surface), alternating knee lifts, quick side steps or lateral leg lifts. Finally, 3 minutes of low-intensity walking to facilitate recovery for the next phase of training.

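### No analysis model is named; regressing T1 on arm and T0 instead of the implied group-by-time test cuts variance about 23% at the plan's own correlation, with no extra data

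*Combined protocol and SAP*

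**What the plan says.** The only statistical text is the section Sample numerosity. It states that "G*Power software (version 3.1) was used to determine the sample size needed to ensure adequate statistical power", with effect size f = 0.25, significance level 0.05, power 0.85 and a nonsphericity correction of 1. It adds that "two groups (multicomponent training and aerobic training) and two measurement times (before and after the intervention) were considered" and that "An average correlation (0.5) was estimated between the repeated measurements on participants". The result is a "sample size of 32-40 total participants, with 16-20 participants per group". The test entered in the software is not named. No analysis model, covariate or primary test appears anywhere else in the document.

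Three other statements bear on the point:

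- Participants: "The study aims to recruit at least 60 cancer survivors". That is 20 per arm if the three arms are equal, which is an assumption.
- Procedures, Data collection: every subject is assessed at T0 (before the intervention) and T1 (at its end).
- Experimental Design: "After initial evaluations, subjects will be randomly assigned". T0 is therefore measured before allocation. That sentence goes on to mention two groups, whereas Procedures lists three. The conflict needs correcting, but it does not affect the order of baseline and randomisation.

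**The concern.** With a baseline and one follow-up, an analyst could compare T1 values alone, compare change scores (the same as a group-by-time ANOVA), or adjust T1 for T0. The plan leaves this choice open, so it could be made after the data are seen. The sample-size inputs point to the change-score version.

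At a correlation of 0.5 that version is inefficient. Subtracting the whole baseline removes more than the regression of T1 on T0 supports, and so adds noise. ANCOVA estimates how much of the baseline to subtract. Under randomisation both methods target the same between-arm difference, so the issue is precision and not a change of question.

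Precision matters here because the plan accepts as few as 16 per group, where the implied test does not reach the stated 85%, and because no dropout allowance is made for a 24-week programme.

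**Working it through.** **Inputs (Sample numerosity).** f = 0.25, alpha = 0.05, target power 0.85, 2 groups, m = 2 times, correlation rho = 0.5, nonsphericity correction 1, n = 16 to 20 per group.

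**Step 1: reproduce the plan's figure.** For the group-by-time interaction, G*Power uses noncentrality lambda = f² × N × m / (1 − rho) = 0.0625 × N × 2 / 0.5 = 0.25N, with 1 and N − 2 degrees of freedom.

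| N | Power |
|---|---|
| 32 | 78.1% |
| 38 | 85.06% |
| 40 | 86.9% |

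N = 38 is the smallest even total reaching 85%, and it lies inside 32-40. A within-subject test of time has the same lambda and degrees of freedom, so it gives the same N, but it does not compare MCT with AT. A between-group main effect would need 110. The interaction is thus the only candidate that both fits the range and compares the two arms, though this is an inference.

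**Step 2: effect in SD units.** In a 2 × 2 design, f = 0.25 for the interaction is a between-group difference in change of 4f = 1.0 SD.

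**Step 3: variances.** Assume equal SDs at T0 and T1. Per participant:

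- change score: 2(1 − rho)SD² = 1.00 SD² at rho = 0.5;
- ANCOVA: (1 − rho²)SD² = 0.75 SD², times 1 + 1/(N − k − 2) for estimating the slope, with k arms in the model and N the total over those arms.

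The ratio is (1 + rho)/2 × [1 + 1/(N − k − 2)]:

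- two arms, 20 each: 0.75 × (1 + 1/36) = 0.771;
- two arms, 16 each: 0.75 × (1 + 1/28) = 0.777;
- three arms, 20 each: 0.75 × (1 + 1/55) = 0.764;
- three arms, 16 each: 0.75 × (1 + 1/43) = 0.767.

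For two arms the gain equals that from 1/0.771 = 1.30 or 1/0.777 = 1.29 times as many participants.

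**Step 4: power for a 1.0 SD difference** (noncentral distribution, slope cost included, one error degree of freedom fewer for ANCOVA).

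| Design | Change score | ANCOVA |
|---|---|---|
| Two arms, 20 each | 86.9% | 93.9% |
| Two arms, 16 each | 78.1% | 87.3% |
| Three arms, 20 each | 87.5% | 94.5% |
| Three arms, 16 each | 79.0% | 88.4% |

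Simulation with 40,000 runs agreed: 86.9% against 93.9% and 77.8% against 87.1% for two arms; 87.5% against 94.4% and 78.9% against 88.4% for three. The mean 95% CI half-width with two arms of 20 falls from 0.636 to 0.559 SD.

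**Step 5: dependence on the correlation** (two arms, 20 each).

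| rho | Variance reduction |
|---|---|
| 0.3 | 33% |
| 0.5 | 23% |
| 0.7 | 13% |
| 0.8 | 7.5% |
| 0.9 | 2% |
| 0.95 | −0.2% |

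Break-even is at rho = 0.946 (20 per arm) or 0.931 (16 per arm) for two arms, and 0.964 or 0.955 for three. At rho = 0.95 with two arms of 16, ANCOVA loses about 1%.

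**Step 6: dependence on the SD ratio** s = SD(T1)/SD(T0). The ratio becomes s²(1 − rho²)/(1 + s² − 2·rho·s) × [1 + 1/(N − k − 2)]. At rho = 0.5 with two arms of 20, the reduction is 41% at s = 0.8, 23% at 1.0, 10% at 1.2, 6% at 1.3 and 1% at 1.5.

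**The case against.** - **The comparator is inferred.** No test is named, and if the calculation was for the time factor, f = 0.25 is not a 1.0 SD difference between arms. The absolute power figures would then lose their basis. This stands as a caveat. The variance ratio does not depend on f, and the absence of a model is a fact on either reading.
- **Equal SDs are assumed.** This also stands: Step 6 shows the 23% is not a fixed quantity. But the plan's own calculation assumes a common SD, and over ratios from 0.8 to 1.5 ANCOVA gains or roughly breaks even.
- **At 60 recruited and equally split, the implied test already has 87%.** True. The shortfall to 78% arises only at 16 per group, but the plan itself accepts that number. It is also what remains of 20 after an assumed 20% loss.
- **ANCOVA does not deal with dropout.** Correct. It recovers precision, not bias from differential loss, and as a complete-case model it omits anyone without T1. A repeated-measures model with the baseline means constrained equal across arms would give similar precision and keep those participants.
- **Multiplicity, the lack of a single primary outcome and small-group sessions are untouched.** Also correct, but the change makes none of them worse. The power figures are for one unadjusted contrast at a large effect. At 0.5 SD and 20 per arm, power is 34% with change scores and 42% with ANCOVA, inadequate either way.

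**Conclusion.** The concern holds. The plan specifies no model, and the one its sample-size inputs imply is less precise than a baseline-adjusted model that uses the same data. At the plan's correlation of 0.5 the variance reduction is 22-24% across 16 to 20 per arm and two or three arms (25% in the large-sample limit). For a 1.0 SD difference, ANCOVA meets the stated 85% power at both ends of the accepted range, while the implied test meets it only near the top.

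The size rests on equal SDs at T0 and T1, a roughly linear T0-T1 relation, the group-by-time reading of the calculation, and a correlation of 0.5 that the plan applies to all outcomes without a source. The direction is sturdier: with equal SDs, ANCOVA is at worst about 1% less efficient at a correlation of 0.95. The trial is not invalid without this change, but the change should be made.

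**What to change.** Add to the protocol, for each outcome, a linear model of the T1 value on randomised arm (MCT, AT, WLCG) and the T0 value, reporting adjusted mean differences with 95% confidence intervals. Specify it in place of a group-by-time ANOVA and before any outcome data are examined. Keep the recruitment target: the gain is a margin against losses and an uncertain correlation, not grounds for a smaller sample.

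The cost is one sentence and one degree of freedom per model, which the figures above already include. No new measurements, visits or participants are needed. The handling of missing T1 values still has to be stated separately.

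### The stated inputs give 38 participants (19 per group), not 32-40; 32 gives 78% power instead of 85%, and nothing is allowed for dropout

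*Combined protocol and SAP*

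**What the plan says.** The section SAMPLE NUMEROSITY describes a G*Power 3.1 calculation "assuming a mean effect (with a value of 0.25 for effect size f"). It continues: "A significance level of 0.05 was set", and "a statistical power of 85% (0.85) was adopted". On the design, "two groups (multicomponent training and aerobic training) and two measurement times (before and after the intervention) were considered". On the correlation, "An average correlation (0.5) was estimated between the repeated measurements on participants". The nonsphericity correction is set to 1. The section then says that, on these parameters, "the calculation indicated the need for a sample size of 32-40 total participants, with 16-20 participants per group".

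Three other places bear on the point. PARTICIPANTS gives the recruitment target: "The study aims to recruit at least 60 cancer survivors". PROCEDURES assigns participants to three groups (MCT, AT and the waiting-list control) without stating a ratio. The secondary outcome is "To assess adherence to protocols through analysis of dropout rates and number of sessions completed". The intervention lasts 24 weeks (Experimental Design). The sample-size section mentions no dropout allowance.

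**The concern.** Every input is a single value, so the calculation should return a single sample size. The plan reports a range, varies no input to produce it, and gives no reason for its width. If the true requirement lies above 32, the lower end does not deliver the stated power.

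This matters because of attrition. By calling 16 per group sufficient, the plan implies that an arm of 20 can lose four people (20%) with no loss of the stated power. If that is untrue, the MCT versus AT comparison has almost no reserve, and the plan would not show it.

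**Working it through.** **Inputs** (all from SAMPLE NUMEROSITY): f = 0.25; alpha = 0.05; target power 0.85; k = 2 groups; m = 2 times; correlation rho = 0.5; epsilon = 1. Equal groups are implied by the per-group figures.

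**Option assumed.** The plan does not name the G*Power test. A correlation between repeated measures together with a nonsphericity correction points to repeated-measures ANOVA with a within-subject effect, so I used the within-between interaction. With two groups and two times, the within-factor main effect gives the same numbers.

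**Formula.** Noncentral F with

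- lambda = f² × N × m × epsilon / (1 − rho) = 0.0625 × N × 2 / 0.5 = 0.25N
- df1 = (k − 1)(m − 1) = 1
- df2 = (N − k)(m − 1) = N − 2

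**Power by MCT + AT total with T1 data**

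| Total N | Per group | lambda | Power |
|---|---|---|---|
| 32 | 16 | 8.0 | 78.1% |
| 34 | 17 | 8.5 | 80.7% |
| 36 | 18 | 9.0 | 83.0% |
| 38 | 19 | 9.5 | 85.06% |
| 40 | 20 | 10.0 | 86.9% |

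N = 37 gives 84.1%, so 38 is the first total to reach 85%. The plan's upper end (40) is compatible with its inputs; its lower end (32) is six participants short. Even 80% power needs 34.

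**Cross-check.** For a two-sample t test on change scores with N/2 per group, the squared noncentrality is d² × N/4. Setting this equal to 0.25N gives d = 1.0 SD of change. The noncentral t test at d = 1.0 returns the same power values.

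**Could another reading produce 32?** At 85% power:

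- between-groups effect: 110
- alternative effect-size definitions that G*Power offers: about 146 to 148
- three groups: 48
- correlation 0.6 in place of 0.5: 32 (86.4%), but this is not the stated input
- one-sided t test: 86.8% at 32, but the F test has no one-sided form

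None of these supports 32 on the stated inputs.

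**Effect of losses.** Sixty split 1:1:1 (assumed) puts 20 in each arm, so 40 in MCT + AT. Retained participants:

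- 19 and 19: 85.06%
- 20 and 18: 84.96%
- 19 and 18: 84.0%
- 18 and 18 (10% loss): 83.0%
- 17 and 17 (15% loss): 80.7%
- 16 and 16 (20% loss): 78.1%
- 15 and 15 (25% loss): 75.3%

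**Baseline-adjusted ANCOVA, same 1.0 SD difference.** At rho = 0.5 the SD of change equals the raw SD, since √(2 × (1 − 0.5)) = 1. The ANCOVA residual SD is √(1 − 0.5²) = √0.75 of the raw SD, with df = 2n − 3. Power is 83.5% at 14 per arm, 86.2% at 15 and 88.4% at 16, so 15 per arm is the first to pass 85%.

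**The case against.** The strongest reply is that the trial is not planned at 32. The target is at least 60, which is a floor; split equally, it gives 40 in the two exercise arms and 86.9% power, and 38 lies inside the printed range. This stands. The recruitment target is not shown to be wrong for MCT versus AT before dropout; the error is in the stated range and the absent allowance.

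Second, the documents give no dropout rate, so 20% is an assumption. The exclusion of people who foresee being away for more than two weeks offers some protection. Both points are fair, which is why losses are shown from 10% to 25%. The decline is gradual: two losses from one arm leave 84.96%, and 18 per arm costs about two points against the target.

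Third, the G*Power option is inferred, and the answer is sensitive to a guessed correlation: at 0.58, 32 participants would give 84.8%. This shows how soft the inputs are, but it does not rescue a range that the plan attributes to its stated parameters.

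Fourth, correcting the figure does not validate the design behind it. The calculation covers two of the three groups. It also rests on a 1.0 SD difference between two active arms; at 0.5 SD, 20 per arm gives about 34% power (43% with ANCOVA). This also stands, and it limits what the corrected figure can be taken to show.

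**Conclusion.** The concern holds. On the plan's own inputs the requirement is 38 participants with T1 data (19 per group). The lower end of the range gives 78.1% power, so type II error there is about 22% instead of 15%. Starting from 20 per arm, power stays at or above 85% only if no arm loses more than one participant, although the shortfall just past that point is small.

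The conclusion rests on the within-between interaction being the option used and, for the dropout figures, on an equal three-way split of 60. The value 38 itself is firm given the stated inputs. The plan should be corrected, but this does not call the recruitment target into question.

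**What to change.** In SAMPLE NUMEROSITY:

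1. Replace the range with 38 participants with T1 data (19 per group), and name the G*Power option used. If it was a different option, say so and give the single figure it returns.
2. State the power at 20 and at 16 per group (87% and 78%).
3. State an expected retention to T1 and the allocation ratio, so that the step from 60 recruited to the number analysed is visible.
4. Preferably, prespecify a baseline-adjusted ANCOVA for the MCT versus AT comparison. At correlation 0.5 and a 1.0 SD difference it needs 15 per arm and gives 88% at 16 per arm, so a 20% loss from 20 per arm would be covered. The text should say that this depends on those two assumptions.

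The cost is restated figures and one sentence on the analysis. T0 is already measured in everyone, so no new data and no extra patients are needed. If the analysis stays unadjusted for baseline, the plan has to acknowledge somewhat lower power after dropout.

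### The stated 16-20 participants per group do not all give 85% power: the plan's own inputs need 19 per exercise arm with both assessments, and no allowance for loss over 24 weeks is stated

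*Combined protocol and SAP*

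**What the plan says.** All references are to the combined protocol and SAP.

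- **Sample numerosity, error rates:** "A significance level of 0.05 was set and a statistical power of 85% (0.85) was adopted".
- **Sample numerosity, effect size:** a medium effect, "with a value of 0.25 for effect size f".
- **Sample numerosity, design:** "two groups (multicomponent training and aerobic training) and two measurement times (before and after the intervention) were considered". The waiting-list arm (WLCG) is not in the calculation.
- **Sample numerosity, correlation:** "An average correlation (0.5) was estimated between the repeated measurements on participants". The nonsphericity correction is set to 1.
- **Sample numerosity, result:** a total of 32-40, "with 16-20 participants per group, to ensure sufficient statistical power to detect any significant effects".
- **Participants:** "The study aims to recruit at least 60 cancer survivors".
- **Procedures:** random assignment to three groups, with no ratio given, and assessment at T0 and at the end of the intervention (T1). Experimental Design speaks of two groups at randomisation and gives a duration of 24 weeks.
- **Secondary outcome:** "To assess adherence to protocols through analysis of dropout rates and number of sessions completed".

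The sample-size section gives no dropout rate and no inflation for loss, and it does not say whether 16-20 per group means participants randomised or participants with both assessments.

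**The concern.** A single set of power inputs leads to one required number, not to a range whose upper end is 25% above its lower end (40/32 = 1.25). If 85% is the target, part of the range must miss it. A reader of the section would take 16 per arm as sufficient, and could treat a fall from 20 to 16 during the trial as harmless.

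The second gap concerns loss. A before-after comparison between groups draws its information from people measured at both times. T1 is the only assessment after baseline, so someone who leaves before it contributes no change. The section does not say how many such losses the stated power can absorb. At stake is how a null MCT versus AT result would be read: the protocol would claim 85% power for a trial that, at the lower end of its range, has 78%.

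**Working it through.** **Inputs from Sample numerosity.** Effect size f = 0.25; alpha = 0.05; target power 0.85; k = 2 groups; m = 2 times; correlation rho = 0.5; nonsphericity correction 1.

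**Test.** The section names G*Power but not the test. The group-by-time (within-between) F test is the one that addresses MCT versus AT change:

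- noncentrality: lambda = f² × N × m / (1 − rho) = 0.0625 × N × 2 / 0.5 = 0.25N
- degrees of freedom: (k − 1)(m − 1) = 1 and (N − k)(m − 1) = N − 2
- power = probability that a noncentral F(1, N − 2; lambda) exceeds the 5% critical value of the central F(1, N − 2).

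**Reproducing the plan's figure.** The smallest N with at least 85% power is 38, or 19 per group. This lies inside the stated 32-40, so the plan's calculation is recovered, but only the top of the range meets the target.

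| Analysed per arm | N (MCT + AT) | lambda | Power |
|---|---|---|---|
| 20 | 40 | 10.0 | 86.9% |
| 19 | 38 | 9.5 | 85.1% |
| 18 | 36 | 9.0 | 83.0% |
| 17 | 34 | 8.5 | 80.7% |
| 16 | 32 | 8.0 | 78.1% |

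**Is another test behind the range?** With the same inputs, the within-factor (time) test also needs 38. The between-factor test needs 110, and G*Power's two other effect-size conventions for the interaction need 74 and 148. None of those last three falls in 32-40. As a cross-check, lambda = 0.25N corresponds to a between-group difference in mean change of one standard deviation of change. A normal approximation for that difference gives 18 per group, and the exact F test adds one.

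**Margin for loss.** Assume that exactly 60 are randomised 1:1:1. Then 60 / 3 = 20 per arm, and 20 − 19 = 1 loss per arm before 85% is missed, or 1/20 = 5%. For assumed loss rates d, the number analysed per arm is 20 × (1 − d):

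| Assumed loss | Analysed per arm | Power |
|---|---|---|
| 0% | 20 | 86.9% |
| 5% | 19 | 85.1% |
| 10% | 18 | 83.0% |
| 15% | 17 | 80.7% |
| 20% | 16 | 78.1% |

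The documents give no loss rate; 0-20% is a range chosen to show the sensitivity.

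**The case against.** The strongest reply is that the trial recruits 60 or more, well above 32-40, so a cushion exists. This does not stand as put. The 32-40 covers two arms and the 60 covers three, and WLCG participants add nothing to a two-group MCT versus AT calculation. What does stand is that 60 is a minimum, and recruiting more would widen the margin. A different allocation ratio would also change it.

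A second reply is that the effect is small. That is fair: against the stated 85%, 10% loss costs about 2 points, and balanced power stays above 80% up to 15% loss. The exclusion of people who expect to be away for more than two weeks may also limit losses, although it is not an allowance for them. Neither reply rescues the lower end of the range, which fails without any loss.

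A third reply is that a three-group interaction at the same f would need only 48 in total, or 16 per arm. That is correct arithmetic, and it would leave a margin of four per arm, but the section explicitly describes a two-group calculation.

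A reader might also infer more than the documents support:

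- **That the plan recruits exactly the calculated number.** It does not. The target is at least 60, and nothing derives that figure from 32-40 or says what it contains.
- **That the plan expects dropout.** It lists dropout as something to measure and predicts no level.
- **That a shortfall is very likely.** No loss rate is given, so no such probability can be taken from the plan. Counting every case with one arm below 19 would also mislead: arms of 20 and 18 still total 38, with lambda = 20 × 18 / 38 = 9.47 and power 84.96%.
- **That the comparison will be restricted to completers.** The documents define no analysis set, so this would be conjecture, and it is a separate matter.

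**Conclusion.** The point holds in a limited form. The closing sentence of Sample numerosity is wrong as written: 85% power needs 19 per exercise arm with both assessments, and 16 per group gives 78%, about 7 points short with no loss at all. This part rests only on the plan's own inputs and on reading the calculation as the group-by-time test.

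The missing allowance for loss is a smaller matter and is conditional. At exactly 60 randomised 1:1:1 there is room for one loss per arm. Power then falls from 86.9% with no loss to 83.0% at 10% and 78.1% at 20%, with the loss rates assumed. This does not show that the trial will be underpowered. It shows that the 85% is stated without the condition on which it depends.

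**What to change.** Replace the closing sentence of Sample numerosity with:

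> 85% power for f=0.25 needs 19 participants with T0 and T1 in each of MCT and AT; 16 per group gives 78%. With 60 randomised 1:1:1 (20 per arm) power is 87% with no loss, 85% at 5% loss, 83% at 10%, 81% at 15% and 78% at 20%.

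The ratio in this wording is an assumption. The sponsor should confirm it, and recompute the second sentence if a different ratio or a larger total is intended.

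Cost: wording only. The stated power becomes slightly less favourable, and no more participants are needed.

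### Procedures randomises to three groups but Experimental Design to two, and the sample-size paragraph covers MCT versus AT only and, under the test its inputs imply, reaches its 85% power only from 38 in total

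*Combined protocol and SAP*

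**What the plan says.** **Allocation.** Procedures says "Then participants will be randomly assigned to one of three groups" and lists MCT, AT and WLCG. Experimental Design says "After initial evaluations, subjects will be randomly assigned to one of two groups" and does not name the two groups. The same section then describes the third arm: "Participants in the WLCG will not perform any structured physical activity during the entire intervention period". No allocation ratio is given.

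**Comparisons.** The purpose statement names both AT and the WLCG as comparators for MCT. The first hypothesis is "We hypothesize that both groups will demonstrate improvements in physiological parameters, physical fitness, mental well-being, and overall quality of life compared to the WLCG". A greater effect of MCT than of AT comes after it.

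**Sample size.** Sample Numerosity uses G*Power with effect size f = 0.25, significance level 0.05, power 0.85, correlation 0.5 between repeated measurements and a nonsphericity correction of 1. Its scope is explicit: "For the calculation, two groups (multicomponent training and aerobic training) and two measurement times (before and after the intervention) were considered". Its result is that "the calculation indicated the need for a sample size of 32-40 total participants, with 16-20 participants per group". Neither the test nor its sidedness is stated.

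**Recruitment.** Participants says "The study aims to recruit at least 60 cancer survivors". Nothing in the text connects this number with the calculation.

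**The concern.** The protocol gives two allocation rules, and one of them sits in the section that defines the experimental design. Staff carrying out the randomisation, and later readers judging it, should not have to work out which rule applies.

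The sample-size paragraph stops at the same two arms. It says nothing about power for the WLCG comparisons, which come first in the hypotheses, or for a three-group analysis. It also returns a range. With f, alpha, power, correlation, groups and times all fixed, such a calculation returns one number, so at least part of the range cannot correspond to the stated 85%. As written, a reader cannot tell what the three-arm trial is powered to detect.

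**Working it through.** **1. The allocation statements side by side.**

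- Purpose and Hypothesis: the WLCG is a comparator.
- Procedures: three groups, all randomised, WLCG listed.
- Experimental Design: two groups randomised; WLCG participants described a few lines later.
- Sample Numerosity: two groups, MCT and AT.

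No section describes a non-random route into the WLCG.

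**2. The plan's own calculation.** The inputs, all from Sample Numerosity, are f = 0.25, alpha = 0.05, correlation rho = 0.5, k = 2 groups, m = 2 times and nonsphericity correction 1. The test is not stated. Effect size f with a nonsphericity correction implies a repeated-measures F test, and the group-by-time (within-between) interaction is the one that compares change between groups. With total N:

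- noncentrality lambda = f² × N × m / (1 − rho) = 0.0625 × N × 2 / 0.5 = 0.25 N
- df1 = (k − 1)(m − 1) = 1; df2 = (N − k)(m − 1) = N − 2
- power = P(noncentral F > the 95% point of the central F)

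| Total N | Per group | lambda | Power |
|---|---|---|---|
| 32 | 16 | 8.0 | 78.1% |
| 34 | 17 | 8.5 | 80.7% |
| 36 | 18 | 9.0 | 83.0% |
| 38 | 19 | 9.5 | 85.1% |
| 40 | 20 | 10.0 | 86.9% |

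The first total at or above 85% is 38. The upper end of the stated range is consistent with the inputs. The lower end falls short by 85.0 − 78.1 = 6.9 percentage points.

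**3. Other readings of the inputs.** The within-subject main effect also needs 38. A between-group test on the same inputs needs 110. A one-sided 0.05 test (equivalent here to the F test at 0.10) reaches 86.8% at 32.

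**4. What f = 0.25 means here.** For two equal groups compared on change scores, lambda = d² × N / 4, where d is the difference in mean change in SDs of change. Setting this equal to 0.25 N gives d = 1. The calculation therefore assumes a 1 SD difference in change between the two exercise programmes.

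**5. The planned 60.** Equal allocation is assumed, since no ratio is stated: 60 / 3 = 20 per arm, 40 per pair.

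- One unadjusted pair, complete data, 1 SD difference: 86.9%. This applies to each exercise group versus the WLCG only if the same effect is assumed there.
- Same pair, alpha split by Bonferroni over three pairs (0.05 / 3; an assumption): 74.2%. Reaching 85% would then take 52 per pair.
- Same pair, unadjusted, 10% loss (an assumption): 40 × 0.9 = 36 remain, 83.0%.
- Same pair, unadjusted, complete data, smaller illustrative effects: 69% at 0.8 SD and 34% at 0.5 SD.
- Three-group interaction at f = 0.25 (lambda = 0.25 N, df1 = 2, df2 = N − 3): 45 gives 83.4%, 48 gives 86.0%, 60 gives 93.2%. With three equal arms, 48 is the first total to reach 85%.

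The last line is not the same effect as in the pairwise lines. With three groups, f = 0.25 corresponds to a largest pairwise difference in change of 1.06 SD (one arm differs) to 1.22 SD (equally spaced means). If both exercise groups are exactly 1 SD better than the WLCG, 60 gives 90.0%.

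**The case against.** The two-group sentence is very likely a slip. Procedures lists the WLCG among the randomised groups, the purpose statement names it as a comparator, and Experimental Design itself describes it. A reader might infer from the literal wording that the WLCG is filled without randomisation and that comparisons with it are open to selection bias. The documents do not support that: they point to a randomised three-arm trial and give no other way into the WLCG. What stands is a contradiction to be removed, not a demonstrated bias.

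On the calculation, neither the test nor its sidedness is stated, and the hypotheses are directional. A one-sided 0.05 test would justify 32. That is fair, and it is why 38 has to carry its condition. But no one-sided test is stated, and the inputs listed are those of a non-directional F test. Also, 38 lies inside the stated range, so only part of the range is wrong.

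The low end has little practical effect if at least 60 are recruited and split equally, since each pair then has 40. The upper figure of 20 per group times three arms is also exactly 60, so the numbers agree even though the link is not written down. This too stands, and it means the documents do not show an underpowered trial.

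**Conclusion.** The point holds as an error in what is written. The protocol contradicts itself on the number of randomised groups. The sample-size paragraph leaves out the WLCG comparisons of the first hypothesis and does not state its test, its sidedness or its relation to the target of at least 60. Under the two-sided group-by-time F test implied by its inputs, the stated 85% is reached only from 38, and the lower end of 32 gives 78.1%. This conclusion depends on that reading of the test.

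A reader might go further in either direction. One inference is that 60 is too few; the other is that 60 is amply sufficient. The documents support neither. The 86.9% per pair needs equal arms, complete data, no multiplicity adjustment and a 1 SD difference in change. It falls to 83.0% with an assumed 10% loss, 74.2% with a Bonferroni split over three pairs and 69% at 0.8 SD. The plan states no allocation ratio, dropout allowance or multiplicity rule from which to choose among these.

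**What to change.** 1. In Experimental Design, change the allocation sentence to one of three groups (MCT, AT, WLCG), in agreement with Procedures, and state the allocation ratio.
2. In Sample Numerosity, replace the 32-40 range and its per-group figures with: 38 (19 per group) for 85% power on one pairwise contrast, two-sided group-by-time interaction F test, alpha 0.05, equivalent to a 1 SD difference in change. If a one-sided test was in fact intended, say so and justify it.
3. Add the power of the planned 60 together with its conditions: with 20 per arm, complete data and a 1 SD difference in change, 86.9% per unadjusted pairwise contrast, including each exercise group versus the WLCG; 74.2% per pair if alpha is Bonferroni-split over three pairs; 83.0% per unadjusted pair with an assumed 10% loss; and 93.2% for the three-group interaction at f = 0.25, for which 48 are needed for 85%. Label equal allocation and the 10% loss as assumptions unless the sponsor adopts them.

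The cost is one sentence and one rewritten paragraph. Enrolment, visits and assessments do not change.
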